### 5.2 DATA COLLECTION & FOLLOW-UP ASSESSMENTS

The patient will be assessed at baseline. Lactate dehydrogenase (LDH) will be assessed once a week for 4 weeks, then once every 2 weeks for the next month and monthly thereafter; TTE ECHO follow–up will be performed at baseline, at 1 month and at 3 months, followed until study completion per site standard of care. A complete list of data fields to be collected is provided in Appendix II. A summary

of the data collection is provided in Table 1 below, and follow-up assessments are further described in the following sections.

	Baseline 	Once a week 	Once a month 	During regular ambulatory visits	At time of event
Consent Form	х				
Demographics & Medical History	х				
Enrollment form	х				
Laboratory Assessment (study site standard of care)	х		х	х	х
LDH Assessment	х	X 	X 	х	х
ECHO assessment	х		X 	Х	х
Anti-coagulation / anti-platelet regimen	х	Х		х	х
Adverse Events: thrombosis, other adverse events					х
Rehospitalizations / Reoperations					х
Outcome					Х

 Baseline is defined as the time point of the patient enrollment to the study.

 The follow-up assessments commence after the study enrollment.

 LDH assessment once a week for 4 weeks, then once every 2 weeks for the next month and monthly thereafter

 ECHO follow–up will be performed at baseline, at 1 month and at 3 months, followed by periodical 6-monthly examinations

### 5.2.1 Demographics

Patient demographics will be collected at baseline, including age, gender, height, weight, BMI, blood type, vital signs, etiology of heart failure, duration of mechanical circulatory support prior to study enrollment, Modified Rankin Score, INTERMACS Profile prior to HM3 implant, and therapeutic intent of HM3 support.

### 5.2.2 Medical History

The patient's medical history will be collected at baseline, including a history of cardiac arrhythmias, diabetes, smoking, hypertension, and cancer.

### 5.2.3 Enrollment form

Information will be captured on whether the patient met the study inclusion/exclusion criteria.

#### 5.2.4 Laboratory Assessments and Diagnostics

LDH assessment will be performed once a week for 4 weeks after the randomization, then once every 2 weeks for the next month and monthly thereafter; other regular laboratory assessments will include standard of care work-up, including measurements of kidney and liver function and hemostasis. Desirably, the same local authorized laboratory facility should be used by the patients to ensure consistency of a laboratory follow-up.

#### 5.2.4.1 Apixaban plasma concentration

Apixaban peak and trough levels will be performed using a commercially available anti-Xa assay with apixaban calibrators at 4 weeks visit per study protocol. Levels will also be drawn at the time of presentation with any HRAE.

#### 5.2.5 Adverse Events

All INTERMACS adverse event definitions (version 5.0) will be used in this study for the evaluation of primary and secondary objectives. Laboratory values will be determined at the time of an adverse event.

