### 2 STUDY OBJECTIVES

#### 2.1 PRIMARY ENDPOINT

The primary endpoint to evaluate the safety and feasibility of apixaban with the HeartMate 3 LVAS is survival free of major HRAEs (hemocompatibility related adverse events) at 90 days post-enrollment. The primary analysis will compare the apixaban groups (n=30) to control (n=15). A separate analysis will compare the primary endpoint in patients randomized to receive aspirin (n=15) and no-aspirin (n=15) within the apixaban group.

Major HRAEs include:

- Stroke (ischemic/hemorrhagic)
- Pump thrombosis
- Severe bleeding (see Appendix II)
- Peripheral arterial thromboembolic events

HRAEs are influenced by several patient-specific risk factors, including anticoagulation, poor general health, altered circulation, the pump's hemocompatibility, and the presence of other comorbidities (e.g., AF, infections, etc.). In standard use, clinicians balance the risk of stroke and other thromboembolic (TE) events with the increased risk of bleeding when prescribing

anticoagulation or antiplatelet medications. Therefore, a composite endpoint comprising TE, bleeding, and pump-related events were chosen for the analysis.

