### 3.3.2 Adverse events adjudication and outcomes assessment

All suspected or confirmed HRAEs (safety surveillance see Appendix IV) will be promptly reported to and adjudicated by the Expert Advisory Committee to determine individual patient safety to continue with the assigned treatment arm and the overall study safety and eligibility for continuation. All adverse events will be periodically reported to the Institutional Ethics Committee.

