#### Appendix I: Study design flow chart

### Appendix II: Severe Bleeding Definition

#### SEVERE BLEEDING:

Type A: (Meets any of the below)

- Overt bleeding plus hemoglobin drop of 3 to < 5 g/dL(30-50g/L) (provided hemoglobin drop is related to bleed)
- Any transfusion with overt bleeding

Type B: (Meets any of the below)

- Overt bleeding plus hemoglobin drop 5 g/dL (50g/L) or greater (provided hemoglobin drop is related to bleed)
- Cardiac tamponade
- Bleeding requiring surgical intervention for control (excluding dental, nasal, skin, or hemorrhoid)
- Hypotension attributable to bleeding and requiring intravenous vasoactive agents for hemodynamic support
- Intracranial Hemorrhage that does not meet the definition of hemorrhagic stroke

Type C1: Probable fatal bleeding; no autopsy or imaging confirmation but clinically suspicious

Type C2: Definite fatal bleeding; overt bleeding or autopsy or imaging confirmation

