## Appendix III: Data Collection spreadsheet

		At regular	Once	Once	At the time of
	Baseline	ambulatory visits	a week	a month	the event
Baseline info:					
Patient identifier	х				
Date of birth	х				
Gender	х				
Ethnicity	х				
Race	х				
Etiology	х				
Current device strategy	х				
Blood type	х				
Assessment of routine tests done				1	
to evaluate the prothrombotic					
state	х				
Medical History					
INTERMACS Profile at time of					
implant	Х				
Coronary artery disease	X				
Arrhythmia: atrial/ventricular;					
Afib (yes/no)	X				
Ventricular pacing	X				
Cancer	X				
ICD	X				
Stents, location	X				
Myocardial infarction	X				
Diabetes	Х				
Smoking history	X				
Diverticular disease or diagnosed	X				
AVMs	 				
GI Ulcer	X				
Significant carotid stenosis (or if last examination > 12 months					
old)	v				
AEs since pump implant:	x x				
	^				
Enrollment Form	х				
Date enrolled	х				
Incl/excl criteria (yes/no)	х				
Date of study therapy initiation	х				

	Baseline	At regular ambulatory visits	Once a week	Once a month	At the time of the event
Physical Exam					
Heart rate	X				х
Height in cm	X				X
Weight in kg	X				X
BP_MEAN – Doppler	Х				х
Pump parameters (speed, flow,					
PI, power)	Х	X			Х
Laboratory tests					
Creatinine	х	x			х
Urea	х	x			х
Total Bilirubin	х	x			х
Hgb	х	x			х
Hct	х	х			х
WBC (leucocytes)	х	х			Х
PLT	Х	х			х
Verify-now test	Х	х			х
INR	х	х			х
Fibrinogen	х	х			х
aPTT	х	х			х
LDH	х	х	x 	х	х
Plasma free hemoglobin	х	х			х
BNP (or NT Pro BNP)	Х	x			х
Anti Xa apixaban		x 			х
Baseline diagnostics					
ECG (date, rhythm)	х	х			х
Echocardiography	х			x 	х
Carotid ultrasound (if more than					
12 months since last					
examination)	Х				
Implant information					
Date implanted	Х				
Follow-up					
Reoperation for					
bleeding/thrombosis? Date,					
reason	х				х
Date of initial discharge post LVAD implant	х				

	Baseline	At regular ambulatory visits	Once a week	Once a month	At time of event
Current anticoagulation regimen					
(date, medication, dosages)	x	x			Х
Re-hospitalization for					
thrombosis/other AE? Admission					
date, reason, treatment,					
discharge					Х
HRAE					х
Onset date					x
Is event stroke, TIA, or device					
thrombosis					х
If stroke, is it ischemic or					
hemorrhagic?					х
If stroke, head CT examination					Х
If device thrombosis: Hemolysis					
seen? Thrombolytics given?					
Increase in pump power? Pump					
replaced? Other clinical					

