symptoms?					х
Collect laboratory tests listed					
above					Х
Current anticoag/antiplt					
medications					Х
Any change to anticoag/antiplt					
meds? If yes, what					Х
Infection requiring antibx or + BC					Х
Describe event and treatment					х
Resolution date					Х
Other AE					
Onset date					х
Type of event					х
Examination incl. imaging					
methods					Х
Laboratory tests					х
Rehospitalisation/reoperation					х
Treatment					х
Outcome					
Date					Х

	Baseline	At regular ambulatory visits	Once a week	Once a month	At time of event
Type of outcome (expired,					
explanted, transplanted)					х
If expired, cause of death					х

LDH assessment once a week for 4 weeks, then once every 2 weeks for the next month and monthly thereafter

 ECHO follow–up will be performed at baseline, at 1 month and at 3 months, followed by periodical 6-monthly examinations

 Performed at 4 weeks visit after the anticoagulation transition in patient on apixaban only

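### Does the primary endpoint carry two competing definitions of severe bleeding?

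*Protocol*

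**What the plan says.** Protocol 2.1 lists the bleeding component of the primary endpoint as "Severe bleeding (see Appendix II". Appendix II grades severe bleeding as Type A, B, C1 or C2. Protocol 5.2.5 states that "All INTERMACS adverse event definitions (version 5.0) will be used in this study for the evaluation of primary and secondary objectives". The secondary endpoints in Protocol 2.2 and in the SAP are tied to INTERMACS version 5.0, and the bleeding items there are labelled major and GI bleeding. The SAP names severe bleeding in the primary endpoint without repeating the pointer to Appendix II.

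Under Protocol 3.3.2, suspected or confirmed hemocompatibility events "will be promptly reported to and adjudicated by the Expert Advisory Committee"; no definition is named there. In Appendix III the event block asks "Is event stroke, TIA, or device" thrombosis, and ends with general rows such as "Describe event and treatment".

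Protocol 2.1 counts the 90 days from enrollment. Protocol 3.2 describes follow-up as 90 days from the switch to the assigned regimen. The SAP gives no starting point.

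**The concern.** Read literally, 5.2.5 places a second rule over a component that 2.1 has already defined. If the two rules differed, the committee and the analyst could classify the same bleed differently. The documents describe no blinding, so loose classification would leave room for judgement made with knowledge of the arm. Less bleeding is also a main reason given for testing apixaban, so this component matters.

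The data sheet adds to the worry. Its event-type question names stroke, TIA and device thrombosis, but neither severe bleeding nor peripheral arterial thromboembolism, which are two of the four primary components. Some Appendix II criteria, such as "Any transfusion with overt bleeding", have no field of their own. Two different starting points for the 90 days raise a further doubt about which events count.

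**Working it through.** **1. Which definition applies.**

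- The documents contain one definition of severe bleeding, in Appendix II, and 2.1 points to it by name. That is a specific instruction; 5.2.5 is a general one.
- The label differs by endpoint: severe bleeding in the primary, major bleeding in the INTERMACS-defined secondary list. The SAP keeps the same split.
- 5.2.5 has to mention primary objectives. It is the only source of a definition for stroke, pump thrombosis and peripheral arterial thromboembolism in the primary endpoint.
- Appendix II is written to work alongside an outside stroke definition. One Type B criterion is "Intracranial Hemorrhage that does not meet the definition of hemorrhagic stroke", and the Protocol does not define hemorrhagic stroke itself.

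Read together, the texts give one consistent rule: Appendix II for severe bleeding and INTERMACS for everything else.

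**2. Whether the data exist.** Appendix II has 2 (Type A) + 5 (Type B) + 2 (C1 and C2) = 9 criteria. The related rows in Appendix III are:

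| Appendix II criterion | Related rows in Appendix III |
|---|---|
| Two hemoglobin-drop criteria | Hgb at baseline, at visits and at the event |
| Surgical control | Reoperation row ("bleeding/thrombosis? Date" and reason) |
| Two fatal types | Cause of death |
| Transfusion | Treatment under re-hospitalization and under other adverse events |
| Tamponade | Echocardiography at the event |
| Low pressure needing vasoactive drugs | Mean Doppler pressure at the event |
| Non-stroke intracranial bleed | Imaging row under other adverse events |

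None of these rows codes a full criterion, and the last four criteria have no field of their own. Each criterion does have a related row. Protocol 7.1 keeps source data at the site, and 7.3 makes charts, medical records and laboratory records available to the committee on request. Adjudication is therefore not confined to the spreadsheet.

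**3. Start of the 90 days.** Let the switch come g days after enrollment; g is not given. Follow-up to 90 days after the switch ends on day g + 90 from enrollment. For any g of 0 or more, that period contains days 0 to 90 from enrollment, so the endpoint in 2.1 is always observed. Table 1 defines baseline as enrollment and starts follow-up assessments after it. The sheet records both the enrollment date and the date study therapy began. If g were 1 to 14 days (an assumption), the two windows would differ at each end by 1/90 = 1.1% to 14/90 = 15.6% of 90 days.

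**4. Weight of one patient, if the definitions did disagree.**

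- Control: 1/15 = 6.7 points.
- Pooled apixaban: 1/30 = 3.3 points.
- One in each arm, opposite directions: 1/15 + 1/30 = 10.0 points.
- One in each arm, same direction (as when one definition is simply broader): 1/15 − 1/30 = 3.3 points.

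These weights hold for any reclassified patient in a trial of this size. They do not show that a reclassification would occur.

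**The case for a change.** The best case for a change is that precedence is inferred and never written. 5.2.5 expressly reaches the primary objective, the SAP drops the pointer to Appendix II, and the committee is not told which text to use. The event-type question offers TIA, which is only a secondary event, but not severe bleeding. The groups are small: with assumed failures of 0/30 against 2/15, a two-sided Fisher exact test gives p = 0.106, and with 0/30 against 3/15 it gives p = 0.032. One control patient could thus cross a conventional line, and clarifying text would be cheap.

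The textual observations stand: no sentence states precedence, two of four primary components are absent from that row, and 5.2 and 7.1 point to the wrong appendix for the field list, which is Appendix III. The step from there to a biased endpoint does not stand. It needs a real difference between the definitions, which the documents cannot show, and an analyst who sets aside the direct pointer in 2.1. The Fisher figures rest on assumed counts and on a test and threshold that the SAP does not name. The event-type row is followed by sub-questions for stroke and for device thrombosis, so it reads as a branching prompt and not as the list of primary components.

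**Conclusion.** No change to the plan follows. The definition question is a gap that analysts fill sensibly: Appendix II for severe bleeding, INTERMACS version 5.0 for the other components, enrollment as day 0, and source records for bleeding details that the sheet does not code. The wrong appendix references are clerical slips.

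The effect is zero if the two definitions agree on every patient. If they disagreed on one, a proportion would move 6.7 points (control) or 3.3 points (apixaban), but nothing in the documents shows such a patient. This conclusion assumes that the committee follows the pointer in 2.1 and can obtain the records that 7.3 makes available. It would need another look if the committee classified primary-endpoint bleeds by the INTERMACS text and that text proved to differ from Appendix II.

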#### 5.2.6 Changes to the antithrombotic regimen

Any changes to the designated antithrombotic regimen based on randomization algorithm will be documented during the follow-up visits or with the occurrence of an adverse event.

### 5.2.7 Rehospitalizations/Reoperations

Once a patient is admitted to the hospital, details will be collected on the admission date and the reason for the rehospitalization and date of discharge and antithrombotic therapy status.

Reoperations will also be captured, including the date and reason for the reoperation.

#### 5.2.8 Outcome

The patient's outcome (transplanted, expired, explanted or withdrew) and date of outcome will be captured.

### 5.2.9 Completion of study follow up

Upon completion of study follow up, patients will be transitioned back to their pre-study anticoagulation regimen (e.g. warfarin with aspirin).

#### 5.3 DATA ANALYSIS AND STATISTICAL ISSUES

Survival free of a hemocompatibility-related endpoint 90 days will be evaluated. The prevalence (percent of patients with events) and incidence (event rates in events per pt-year) of adverse events and rehospitalizations will be determined.

#### 6 ETHICAL AND REGULATORY CONSIDERATIONS

#### 6.1 INFORMED CONSENT/PATIENT AUTHORIZATION

The patient, before study enrollment, must provide informed consent. The informed consent form, where patient informed consent is captured, must have prior approval from the Ethics Review Board (ERB).

#### 6.2 ETHICS REVIEW BOARD (ERB)

ERB approval will be obtained prior to enrolling any patients in this study. ERB will maintain oversight of the study in accordance with local policies and procedures.

### 7 DATA REPORTING AND RECORD-KEEPING

#### 7.1 DATA REPORTING

The data to be collected are identified in Appendix I. These will be captured by investigators and entered into a Microsoft Office Excel sheet in anonymized form according to local regulatory standards. The investigator must ensure that the study required observations and findings are recorded correctly and completely and in a timely manner. Source data will be maintained by the study site (e.g. in the form of patient medical records) for verification of data listed in the study data tables.

#### 7.2 CONFIDENTIALITY

Patient Confidentiality will be enforced as per General Data Protection Regulation (GDPR) of the EU Directive no. 2016/679 (effective since 25th May 2018).

The patient will be made aware (via the patient authorization) that certain personally identifiable information will be collected as part of this study and will be disclosed outside the hospital. This information will include date of birth, date of death, admission and discharge dates, and dates of treatment. Except when required by law or except by the patient's authorization, the patient will not be identified by name, address or telephone number in the study records disclosed outside of the hospital. In the study records disclosed outside of the hospital the patient will be assigned a unique study code.

### 7.3 MAINTENANCE OF STUDY DOCUMENTATION

The following study documents will be maintained by the study site and be available for periodic review by Abbott or the expert advisory committee per explicit request:

[figure not shown]
- Copy of the Study Protocol
- Ethics Committee Approvals and Correspondence: a copy of all Ethics Committee approvals and any significant correspondence will also be provided Abbott.
- Ethics Committee approved Patient Authorization/Informed Consent Forms: a copy will also be provided to Abbott.
- Signature Verification Form: all study site individuals approved by the investigator to participate in this study and/or complete data entry must sign the Signature Verification Form. This form will be maintained on site.
- Study Agreement: the Investigator and the Institution will complete a Study Agreement prior to patient enrollment. The agreement will identify the investigator's legal and ethical commitments with respect to the conduct of this study.
- Patient Authorization/Informed Consents for each patient enrolled in the study
- Source documentation (such as patient clinic charts, medical records, lab records)

#### Appendix I: Study design flow chart

### Appendix II: Severe Bleeding Definition

#### SEVERE BLEEDING:

Type A: (Meets any of the below)

- Overt bleeding plus hemoglobin drop of 3 to < 5 g/dL(30-50g/L) (provided hemoglobin drop is related to bleed)
- Any transfusion with overt bleeding

Type B: (Meets any of the below)

- Overt bleeding plus hemoglobin drop 5 g/dL (50g/L) or greater (provided hemoglobin drop is related to bleed)
- Cardiac tamponade
- Bleeding requiring surgical intervention for control (excluding dental, nasal, skin, or hemorrhoid)
- Hypotension attributable to bleeding and requiring intravenous vasoactive agents for hemodynamic support
- Intracranial Hemorrhage that does not meet the definition of hemorrhagic stroke

Type C1: Probable fatal bleeding; no autopsy or imaging confirmation but clinically suspicious

Type C2: Definite fatal bleeding; overt bleeding or autopsy or imaging confirmation

## Appendix III: Data Collection spreadsheet

		At regular	Once	Once	At the time of
	Baseline	ambulatory visits	a week	a month	the event
Baseline info:					
Patient identifier	х				
Date of birth	х				
Gender	х				
Ethnicity	х				
Race	х				
Etiology	х				
Current device strategy	х				
Blood type	х				
Assessment of routine tests done				1	
to evaluate the prothrombotic					
state	х				
Medical History					
INTERMACS Profile at time of					
implant	Х				
Coronary artery disease	X				
Arrhythmia: atrial/ventricular;					
Afib (yes/no)	X				
Ventricular pacing	X				
Cancer	X				
ICD	X				
Stents, location	X				
Myocardial infarction	X				
Diabetes	Х				
Smoking history	X				
Diverticular disease or diagnosed	X				
AVMs	 				
GI Ulcer	X				
Significant carotid stenosis (or if last examination > 12 months					
old)	v				
AEs since pump implant:	x x				
	^				
Enrollment Form	х				
Date enrolled	х				
Incl/excl criteria (yes/no)	х				
Date of study therapy initiation	х				

	Baseline	At regular ambulatory visits	Once a week	Once a month	At the time of the event
Physical Exam					
Heart rate	X				х
Height in cm	X				X
Weight in kg	X				X
BP_MEAN – Doppler	Х				х
Pump parameters (speed, flow,					
PI, power)	Х	X			Х
Laboratory tests					
Creatinine	х	x			х
Urea	х	x			х
Total Bilirubin	х	x			х
Hgb	х	x			х
Hct	х	х			х
WBC (leucocytes)	х	х			Х
PLT	Х	х			х
Verify-now test	Х	х			х
INR	х	х			х
Fibrinogen	х	х			х
aPTT	х	х			х
LDH	х	х	x 	х	х
Plasma free hemoglobin	х	х			х
BNP (or NT Pro BNP)	Х	x			х
Anti Xa apixaban		x 			х
Baseline diagnostics					
ECG (date, rhythm)	х	х			х
Echocardiography	х			x 	х
Carotid ultrasound (if more than					
12 months since last					
examination)	Х				
Implant information					
Date implanted	Х				
Follow-up					
Reoperation for					
bleeding/thrombosis? Date,					
reason	х				х
Date of initial discharge post LVAD implant	х				

	Baseline	At regular ambulatory visits	Once a week	Once a month	At time of event
Current anticoagulation regimen					
(date, medication, dosages)	x	x			Х
Re-hospitalization for					
thrombosis/other AE? Admission					
date, reason, treatment,					
discharge					Х
HRAE					х
Onset date					x
Is event stroke, TIA, or device					
thrombosis					х
If stroke, is it ischemic or					
hemorrhagic?					х
If stroke, head CT examination					Х
If device thrombosis: Hemolysis					
seen? Thrombolytics given?					
Increase in pump power? Pump					
replaced? Other clinical					
symptoms?					х
Collect laboratory tests listed					
above					Х
Current anticoag/antiplt					
medications					Х
Any change to anticoag/antiplt					
meds? If yes, what					Х
Infection requiring antibx or + BC					Х
Describe event and treatment					х
Resolution date					Х
Other AE					
Onset date					х
Type of event					х
Examination incl. imaging					
methods					Х
Laboratory tests					х
Rehospitalisation/reoperation					х
Treatment					х
Outcome					
Date					Х

	Baseline	At regular ambulatory visits	Once a week	Once a month	At time of event
Type of outcome (expired,					
explanted, transplanted)					х
If expired, cause of death					х

LDH assessment once a week for 4 weeks, then once every 2 weeks for the next month and monthly thereafter

 ECHO follow–up will be performed at baseline, at 1 month and at 3 months, followed by periodical 6-monthly examinations

 Performed at 4 weeks visit after the anticoagulation transition in patient on apixaban only

